10. ADVERSE EVENT REPORTING

The following section relates to adverse event reporting in the UK. Australian sites will report their events to the trial office at the University of Newcastle and the process is explained in the country-specific protocol for Australia.

10.1. Reporting Requirements

The collection and reporting of Adverse Events (AEs) will be in accordance with the Research Governance Framework for Health and Social Care and the requirements of the HRA. Definitions of different types of AEs are listed in the table of abbreviations and definitions. The Investigator should assess the seriousness and causality (relatedness) of all AEs experienced by the trial participant and this should be documented in the source data with reference to the protocol.

10.2. Adverse Events

AEs are commonly encountered in patients undergoing an emergency laparotomy. As the safety profile of the SUNPD used in this trial is well characterised, it is highly unlikely that this trial will reveal any new safety information relating to this intervention.

Therefore, the recording of selected AEs will not affect the safety of participants or the aims of the trial. For this reason, only AEs that may be related to the intervention (i.e. until 30-days post-surgery) will be collected on the Day 7 and Day 30 wound assessment CRFs.

AEs that may be related are:

- Skin reaction to the applied dressing
- Pain/discomfort related to the applied dressing

SSI/wound complications do not need to be reported as this data will be captured during routine CRF collection.

Participants may suffer from other complications from their surgery but if these are not related to their wound or the dressing, they do not need to be reported.

10.3. Serious Adverse Events

All events which meet the definition of serious, Serious Adverse Events (SAE), will be collected and recorded in the participant notes. They will also be reported on the SAE form unless otherwise excluded as detailed below. SAEs will be reported to the trial office immediately and within 24 hours of being made aware of the event.

As the dressings being tested in this trial are available and often used within the NHS and Australian Health care system, there are no Serious Adverse Events which would be anticipated as a unique consequence of participation in the trial. We would, however, expect the following events to always be reported as SAEs:

- Enterocutaneous fistula
- Fascial dehiscence
- Death

The following events are **excluded from reporting** to the SUNRISE Trial Office and should be recorded within the participant's notes only:

- SAEs that are related to a pre-existing condition
- SAEs that are related to symptoms or progression of the participant's disease
- Pre-planned hospitalisation

Within SUNRISE, the following events are regarded as SAEs but are **not subject to expedited reporting** using the SAE form. They are expected potential complications of an emergency laparotomy and will be captured on the routine follow-up CRFs:

- Interventions (either within theatre, radiology department or on the ward) to drain wound infections
- Prolonged hospital stay or re-admission as a result of wound complications
- Anastomotic leak
- Intra-peritoneal collections (with or without intervention)
- Thrombo-embolic events
- Infections not related to the wound (e.g. pneumonia, urinary tract infections)
- Cardiac or central nervous system complications
- Paralytic ileus

These events, which meet the definition of serious but are not subject to expedited reporting using the SAE form will be collected and recorded in the participant's notes and on the Wound Assessment CRFs on Day 7 and Day 30.

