9.2. Secondary Outcomes

- Length of hospital stay after surgery as measured from the date of index surgery to the date of discharge

- Wound complications within 30 days post-surgery as graded by Clavien-Dindo scale (see Appendix 2)
- Hospital re-admission for wound related complications within 30 days. These will include SSIs, wound breakdown/dehiscence, seromas and wound related pain
- Health-related Quality of Life assessed using the validated Short Form-12 (SF-12) questionnaire at baseline, and day 7 and day 30, and the EuroQuol-5 Dimension-5 Level (EQ-5D-5L) at baseline, day 7, day 14, day 21 and day 30. Pain at the site of the primary laparotomy will also be assessed, using a Likert scale of 1-10 at day 7 and day 30
- Serious adverse events up to 30 days
- Cost-effectiveness assessed using a patient diary for patient reported healthcare resource usage. Healthcare usage will be taken directly from the patient diaries and the costs attributable to this will be identified
- Patient acceptability of use of their dressing via an acceptability score using a Likert scale of 1-10 at day 7, reflecting participant's assessment of the acceptability of having the dressing
- In the UK only, Health professional's acceptability of use of SUNPD (via a survey of users). This will focus on the ease of application of the dressing, the care needed to maintain/monitor the dressing while it is in place and an overall assessment of health professional's experience of the dressing

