9.4. Schedule of Assessments

Activity/CRF		Pre-theatre	In-theatre	Day 7 post-op (-2/+3 days)	Day 14 post-op (± 2 days)	Day 21 post-op (± 2 days)	Day 30 post-op (+ 14 days)	Day 30+
Patient identification and screening		On-call surgical team						
Patient consent	• Standard	Patient & Member of the research team						
	• Delayed (UK only)	Consultee/Representative & Member of the research team		Patient & Member of the research team when capacity regained				
Randomisation form		Started pre-theatre by the research team	Surgeon or member of the research team					
In-Theatre form			Ideally an operating surgeon, or member of the research team					
Wound Assessment Day 7 or on Discharge (if sooner)^{1,2}				Member of the research team				
EQ-5D-5L		Completed by the participant		Completed by the participant	Completed by the participant	Completed by the participant	Completed by the participant	
SF-12		Completed by the participant		Completed by the participant			Completed by the participant	
Patient diary				Completed daily by the participant following discharge from hospital until they undergo the Day 30 wound review				Patients to continue with a diary if they have an ongoing SSI
Bluebelle wound healing questionnaire							Completed by the participant independently, and then by the participant with a blinded member of the research team reviewing wound	
Wound Assessment Day 30¹							Completed by a blinded member of the research team as an in-person or remote (video) review	
SAE reporting			All serious adverse events by member of the research team using SAE form or wound assessment CRF if excluded from expedited reporting					Related serious adverse events only
Return to theatre form			Member of the research team for any return to theatre following patient returning to theatre					
PI Declaration form for CFR data								Completed by PI at the end of each participant's involvement

¹ Assessment of pain undertaken by a member of the research team by asking the participant and recording the response on the CRF

² Score of patient acceptability of dressing undertaken by a member of the research team by asking the participant and recording the response on the CRF

Table 1: Table of assessments. Member of the research team is a person named on the local delegation log and given the assigned duty.

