10.8. Data Monitoring Committee

The independent Data Monitoring Committee (DMC) will review all SAEs.

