14.2.2. Secondary Outcome Measures

The secondary outcomes for the trial include continuous, categorical and time to event data items.

Time to Event outcomes (Length of hospital stay after surgery):

These outcomes will be compared between treatment groups using survival analysis methods. Kaplan-Meier survival curves will be constructed for visual presentation of time-to-event comparisons. Mixed effects Cox proportional hazard models will be fitted to obtain treatment effects which will be expressed as hazard ratios with 95% confidence intervals.

Categorical outcomes (Wound complications, Hospital readmission for wound related complication(s), Serious Adverse Events):

For binary secondary outcomes, the number and percentage of participants reporting each outcome will be reported by treatment group. An adjusted relative risk and 95% confidence interval will be estimated from a mixed effects log-binomial regression model.

Continuous outcomes (QoL measures - SF-12 and EQ-5D, Likert scale for pain):

SF-12, EQ-5D-5L and the Likert scale for pain at the site of the primary laparotomy are all continuous data outcomes and therefore will be summarised using means and standard deviations. The data at both day 7 and day 30 will be compared between groups using mixed effects linear regression models to obtain an adjusted mean difference and 95% confidence interval. Data for the EQ-5D-5L is collected at baseline and days 7, 14, 21 and 30, and so as a secondary analysis this outcome will also be analysed using a mixed effects repeated measures model.

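### SAEs attributed to the underlying disease or a pre-existing condition stay in site notes, although the schedule, the DMC remit and the SAE outcome cover all SAEs

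*Protocol*

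**What the plan says.** Protocol section 10.3 creates three routes for an SAE.

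- **SAE form.** This is the default. Enterocutaneous fistula, fascial dehiscence and death are expected always to be reported. Appendix 2 also sends death (Clavien-Dindo grade V) to the SAE form.
- **Day 7 and Day 30 wound assessment CRFs, not expedited.** Eight kinds of expected complication take this route, among them anastomotic leak, thrombo-embolic events, non-wound infections, and cardiac or central nervous system complications.
- **Notes only.** This route includes "SAEs that are related to a pre-existing condition" and "SAEs that are related to symptoms or progression of the participant's disease". They are excluded from reporting "to the SUNRISE Trial Office and should be recorded within the participant's notes only".

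Other sections describe SAE capture without the third route.

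- Section 9.4, up to day 30: "All serious adverse events by member of the research team using SAE form or wound assessment CRF if excluded from expedited reporting".
- Section 10.8: "The independent Data Monitoring Committee (DMC) will review all SAEs".
- Section 9.2 lists as a secondary outcome "Serious adverse events up to 30 days", with no limit by cause. Section 14.2.2 includes it under "Categorical outcomes (Wound complications, Hospital readmission for wound related complication(s), Serious Adverse Events", to be summarised by arm and compared by an adjusted relative risk.

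On attribution, section 10.1 states: "The Investigator should assess the seriousness and causality (relatedness) of all AEs experienced by the trial participant".

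**The concern.** An event held only in site notes does not reach the Trial Office, so it reaches neither the trial database nor the DMC. The SAE outcome and the DMC review are described as covering all SAEs but would cover a subset. The statistical analysis plan cannot repair this, because it cannot analyse events that were never collected.

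The subset is formed after randomisation, by a judgement of cause. If that judgement differed between arms, the comparison of recorded SAEs would be distorted. If it did not, SAEs would still be under-counted and the DMC's view would be incomplete. The primary outcome is not affected.

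**Working it through.** **The passages side by side.** Take an SAE that is on neither the always-reported list nor the list of eight, and that the site attributes to the presenting disease. Section 10.3 puts it in the notes only. Section 9.4 puts it on the SAE form or the wound CRF. Section 10.8 has the DMC review it. Section 9.2 counts it in the outcome. A site that follows 10.3 cannot satisfy the other three.

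**Events that fit two lists.** A cardiac event due to a pre-existing condition is on the CRF list by type and on the notes-only list by cause. Section 10.3 gives no order of precedence, so two sites could handle the same event differently.

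**Who decides, and who checks.**

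- The Investigator judges relatedness (10.1).
- The operative team randomises in theatre (7.3).
- Blinding is described only for the Day 30 wound assessor (7.5).
- The Chief Investigator's independent causality review begins on receipt of an SAE form (10.6), so notes-only events bypass it.
- Section 10.4 makes its continuing rule for SAEs possibly related to the SUNPD subject to the 10.3 exclusions. An event linked both to the dressing and to a pre-existing condition has no clear route.

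**Size.** The protocol gives no SAE rate and no share excluded, so there is no figure to reproduce. Everything below is assumed, for illustration.

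- p = true SAE risk, the same in both arms (0.30)
- s = share of SAEs open to exclusion by attribution
- e_C, e_S = proportion of those excluded in control and with SUNPD
- Recorded risk = p × (1 − s × e)
- Apparent relative risk = (1 − s × e_S) / (1 − s × e_C); p cancels

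Results:

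- **Equal exclusion, e_C = e_S, any s:** relative risk 1.00, with under-counting in both arms.
- **s = 0.25, e_C = 0.40, e_S = 0.30:** control 0.30 × (1 − 0.10) = 0.270; SUNPD 0.30 × (1 − 0.075) = 0.2775; 0.2775 / 0.270 = 1.03.
- **s = 1, e_C = 0.40, e_S = 0.30:** control 0.30 × 0.60 = 0.18; SUNPD 0.30 × 0.70 = 0.21; 0.21 / 0.18 = 1.17.
- **Extreme, s = 1, e_C = 0.60, e_S = 0.40:** control 0.30 × 0.40 = 0.12; SUNPD 0.30 × 0.60 = 0.18; 0.18 / 0.12 = 1.50.

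If attribution ran the other way, the ratios would invert: 1 / 1.17 = 0.86 for the third case. The formula treats each participant as having at most one SAE. Section 14.2.2 counts participants, so someone with another captured SAE is counted anyway, which makes the effect smaller.

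**The case against.** The strongest reply is that this is proportionate reporting. The dressing is in routine use with a well-characterised safety profile (10.2, 10.3), and all SAEs in 10.8 could be shorthand for all reportable SAEs. The DMC's outcomes are left to a separate template (16.5). This justifies not expediting such events, and the fix leaves that untouched. It does not explain a notes-only route beside 9.4, which sends events excluded from expedited reporting to the CRF. If reportable SAEs were meant, the text does not say so.

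Several stronger readings are tempting and are not supported.

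- *A reader might infer that deaths from disease progression are lost.* Section 10.3 expects death always to be reported, and Appendix 2 sends it to the SAE form without exception by cause.
- *A reader might infer that the whole SAE comparison depends on attribution.* The eight CRF-listed complications are defined largely by event type, and any return to theatre within 30 days has its own form (8.4). These, with the three always-reported events, cover much of the serious morbidity the protocol anticipates.
- *A reader might infer that attribution is known to differ by arm.* The protocol does not say in words that those attributing SAEs are unblinded; this is inferred from 7.3, 7.5 and 10.1. The judgement concerns the disease, not the dressing, and a blinded team member completes the Day 30 wound assessment (9.4). Differential exclusion is possible but not shown.

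Section 10 describes UK reporting. The Australian procedure is in a country-specific protocol not shown here, so the point is made for UK sites.

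**Conclusion.** The contradiction stands on the text: the notes-only rule in 10.3 cannot be followed together with 9.4 and 10.8, and it leaves the 30-day SAE outcome incomplete. The gap is limited to SAEs outside the always-reported and CRF-listed categories, and to events that fit two lists.

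The size and direction of any bias are unknown. The range from 1.00 through 1.03 to 1.17, and 1.50 under extreme assumptions, rests wholly on assumed inputs. The value 1.17 requires every SAE to be open to exclusion, which the protocol's own lists rule out, so it should not be read as an estimate. Nor do the documents support saying that the safety objective cannot be met. Deaths, the listed complications and dressing-related skin reactions and pain (10.2) are all collected. The narrower conclusion is that an outcome and a DMC review described as covering all SAEs will not do so. This should be corrected.

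**What to change.** 1. Keep the exclusions from expedited reporting. Record the SAEs now kept in the notes only, up to day 30, as non-expedited lines on the Day 7 and Day 30 CRFs, whatever the attributed cause.
2. State in 10.3 which list takes precedence when an event fits two.
3. Use this full set for the SAE secondary outcome and the DMC reports.
4. Reconcile 9.4, 10.3, 10.4 and 10.8, including what the cross-reference in 10.4 to the 10.3 exclusions covers.
5. For participants already recruited, either complete the new lines from the notes or report SAEs by the definition in force at the time, so that two definitions are not mixed without saying so.

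If the sponsor prefers not to collect these events, the outcome in 9.2 and 14.2.2, the SAE row in 9.4 and the DMC remit in 10.8 must be relabelled as reported SAEs only.

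The cost is a CRF and wording change and modest extra data entry for events already in the notes, plus a retrospective notes review if earlier participants are completed. No extra expedited reports are needed.

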10.4. Reporting period

Details of all AEs that are being monitored as defined in sections 10.2 and 10.3 will be documented in source data and, where applicable, reported from the date of randomisation until 30 days post-surgery. SAEs that are judged to be at least possibly related to the use of the SUNPD (unless they are excluded in section 10.3) must still be reported in an expedited manner irrespective of how long after the SUNPD was used the event occurs.

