10.6. Reporting Procedure – UK Trial Office

On receipt of a SAE form from the site, the BCTU trials team will allocate each SAE form with a unique reference number and enter this onto the SAE form in the section for office use only. The SAE form (containing the unique reference number completed) will be forwarded to the site as proof of receipt within 1 working day. The SAE reference number will be quoted on all correspondence and follow-up reports regarding the SAE and filed with the SAE form in the Trial Master File (TMF).

On receipt of an SAE form, the Chief Investigator (CI) or delegate(s) will independently determine the seriousness and causality of the SAE. An SAE judged by the PI or CI or delegate(s) to have a reasonable causal relationship with the intervention will be regarded as a related SAE. The causality assessment given by the PI will not be downgraded by the CI or delegate(s). If the CI or delegate(s) disagrees with the PI's causality assessment, the opinion of both parties will be documented, and where the event requires further reporting, both opinions will be provided in the report.

The CI or delegate(s) will also assess all related SAEs for expectedness. If the event is unexpected (i.e. is not defined in the protocol as an expected event) it will be classified as an unexpected and related SAE. Events which are assessed as both related and unexpected will be classified as Unexpected and Related Serious Adverse Event.

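### At UK sites, section 10.3 keeps SAEs attributed to disease or a pre-existing condition in the notes only, contradicting 9.4 and 10.8 and leaving the compared 30-day SAE outcome as a site-selected subset

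*Protocol*

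**What the plan says.** Protocol 9.2 lists SAEs to 30 days as a secondary outcome. Section 14.2.2 places them among the categorical outcomes, to be compared by an adjusted relative risk from a mixed effects log-binomial model.

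Section 10, which its opening paragraph limits to UK reporting, sorts SAEs in 10.3 into three routes:

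- **SAE form.** This is the default. Enterocutaneous fistula, fascial dehiscence and death are expected always to be reported.
- **Day 7 and Day 30 wound assessment CRFs.** A list of expected complications takes this route instead of the form: wound drainage, wound-related prolonged stay or re-admission, anastomotic leak, intra-peritoneal collections, thrombo-embolism, non-wound infections, cardiac and central nervous system complications, and ileus.
- **Notes only.** This covers "SAEs that are related to a pre-existing condition", "SAEs that are related to symptoms or progression of the participant's disease" and pre-planned hospitalisation. These are excluded from reporting "to the SUNRISE Trial Office and should be recorded within the participant's notes only".

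The schedule of assessments in 9.4 has two routes, not three: "All serious adverse events by member of the research team using SAE form or wound assessment CRF if excluded from expedited reporting". Section 10.8 states: "The independent Data Monitoring Committee (DMC) will review all SAEs".

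**The concern.** Exempting expected or background events from expedited reporting is ordinary practice, and 10.3 does it properly for the listed complications by giving them a CRF route. The two attribution-based categories get no such route. They are absent from the trial data for an outcome that is compared between arms.

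Two things are at stake. First, the protocol promises a 30-day SAE comparison and a DMC review of all SAEs, and following 10.3 delivers neither in full. Second, whether an event is counted depends on what the site thinks caused it, and site staff can know the allocation. If attribution differed between arms, for whatever reason, the SAE relative risk would shift without any true difference in events.

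**Working it through.** No figure in the protocol is disputed, so the check is mainly textual.

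**1. Do the sections agree?** Take an SAE in the first 30 days that the UK site attributes to the patient's underlying disease.

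| Section | Where the event goes |
|---|---|
| 9.4 | SAE form or wound assessment CRF |
| 10.3 | Hospital notes only |
| 10.8 | Reviewed by the DMC |
| 9.2, 14.2.2 | Counted in the compared outcome |

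Under 10.3 the event reaches neither the form nor the CRF, so the other rows fail for it.

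**2. Who makes the judgement, and is it checked?** The Investigator assesses causality (10.1). The operative team randomises in theatre (7.3). Participants and Day 7 assessors are not blind; the Day 30 assessor is (7.5). The central assessment is triggered by a form: "On receipt of an SAE form, the Chief Investigator (CI) or delegate(s) will independently determine the seriousness and causality of the SAE". An event that is never sent is never reassessed.

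**3. Do the lists overlap?** Section 1.2.1 describes patients operated on for obstruction, perforation, ischaemia or abdominal sepsis. A post-operative collection in such a patient is on the CRF list, but a site could also see it as a manifestation of the presenting disease. A cardiac complication in a patient with heart disease fits both the CRF list and the pre-existing-condition exclusion. Section 10.3 gives no order of precedence.

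**4. What does 10.4 add?** It requires expedited reporting, without time limit, of "SAEs that are judged to be at least possibly related to the use of the SUNPD (unless they are excluded in section 10.3", and closes the bracket there. Read literally, an event judged possibly related to the dressing and also attributed to disease is exempt.

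**5. Illustration of size.** All rates here are assumptions; the protocol gives none. Let b be the true risk of a non-wound SAE, the same in both arms; u the share of those SAEs open to notes-only treatment; and d the fraction of that share so treated. The counted risk is b(1 − ud).

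If d is equal in both arms, the factor (1 − ud) cancels and the relative risk stays at 1.00. Events are lost, and wound events then weigh more in an any-SAE result.

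If d differs, take b = 0.30, with d = 0.40 in control and 0.50 in SUNPD:

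| u | Control | SUNPD | RR | Chance of p<0.05 |
|---|---|---|---|---|
| 0.2 | 0.30 × (1 − 0.08) = 0.276 | 0.30 × (1 − 0.10) = 0.270 | 0.98 | about 5% |
| 0.5 | 0.30 × (1 − 0.20) = 0.240 | 0.30 × (1 − 0.25) = 0.225 | 0.94 | about 8% |
| 1.0 | 0.30 × (1 − 0.40) = 0.180 | 0.30 × (1 − 0.50) = 0.150 | 0.83 | about 22% |

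The last column uses a two-sided 5% test of two proportions with 420 per arm. For u = 0.5 the standard error is √[(0.240 × 0.760 + 0.225 × 0.775)/420] = 0.029 and z = 0.015/0.029 ≈ 0.51, which gives about 8%. Using 420 per arm applies the UK rule to every participant, Australians included, which the protocol does not establish. A lean in the other direction inverts the relative risks.

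**The case against.** The strongest reply is that little is lost. Many of the serious complications to be expected after emergency laparotomy are named on the CRF list, and death, fistula and fascial dehiscence are protected. The notes-only class is then mainly a residue, so the low-u rows of the illustration are the more plausible ones. The overlap also has a natural reading: 10.3 calls the listed events complications of the operation, and a post-operative collection or ileus is more readily that than disease progression. All of this stands. It limits the size of the problem but does not reconcile 10.3 with 9.4 and 10.8.

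It can also be said that the exclusion is deliberate, since 10.4 repeats it, and that 9.4 and 10.8 are loose summaries. That may be so. In that case those sections and the outcome label are what need correcting.

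A reader might infer several stronger things that the protocol does not support:

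- **That the SAE relative risk will be biased.** Nothing in the protocol shows that staff would attribute comorbidity or disease events differently because of a skin dressing. The possibility is open because attribution can be unblinded, but the gap in the illustration is assumed. The blinded Day 30 assessor limits the problem for events first considered then, though not for inpatient events sorted earlier.
- **That the rule covers the whole trial.** Section 10 describes UK reporting. The Australian procedure is in a country-specific protocol that is not shown.
- **That the events are irrecoverable.** Section 10.3 requires them in the notes, so they can be extracted, and an analysis plan could define the outcome as reportable SAEs.
- **That 10.4 removes device-related events from the 30-day outcome.** The sentence mainly extends reporting beyond 30 days, and an event judged possibly related to the dressing would not usually also be put down to disease. The bracket is unsafe wording for a safety rule, not evidence of lost outcome data.

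**Conclusion.** The point holds as a minor one. At UK sites, 10.3 conflicts with 9.4 and 10.8. Under 10.3, the compared outcome is SAEs that the site did not attribute to disease or a pre-existing condition, with the attribution possibly unblinded and not centrally checked. The contradiction rests on the text alone and needs no assumption.

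The effect on the comparison cannot be sized from the protocol, and its direction is unknown. Under the assumed rates above, the null relative risk ranges from 0.98, when only a fifth of non-wound SAEs are open to exclusion, to 0.83, when all are. It stays at 1.00 whenever attribution is equal. These figures show how the result depends on the assumptions and are not estimates. The primary outcome is not affected.

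**What to change.** - **10.3, capture.** Keep the two attribution-based categories exempt from the SAE form, but record them by type on the existing Day 7 and Day 30 CRFs whatever the attributed cause. Pre-planned hospitalisation can stay excluded.
- **10.3, precedence.** State that the always-reported list and the CRF list override the exclusions.
- **10.4.** Limit the carve-out so that an SAE judged possibly related to the SUNPD is reported even if it is also attributed to disease or a pre-existing condition.
- **Australia.** Check that the country-specific protocol uses the same rule, because one DMC and one analysis cover both countries.
- **Participants already followed up.** Extract these SAEs from the notes. If that is not feasible, label the outcome and the DMC tables as reportable SAEs, excluding those the site attributed to disease or a pre-existing condition, and align 9.4 and 10.8 with that label.

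The comparison in 14.2.2 needs no change. The cost is wording in two sections, one added line on two existing CRFs, and a notes review if the retrospective step is taken. The downside is slightly more recording at sites and more background events, which pull an any-SAE relative risk towards 1.
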